7.2.2. Deaths

- In subjects in the enrolled population who died within 90 days after entry or before the end of the safety follow-up period, a list will be created for the reason for death, start date of treatment, end date of treatment, date of death, number of days from entry to death, number of days from treatment completion to death, and other information.

7.3. Composition of Analysis Populations

The following analyses will be conducted in all subjects. These analyses except listings will also be conducted by country.

- The inclusion of subjects in each analysis population will be tabulated in each treatment arm. The reason for exclusion will also be tabulated.

7.4. Deviation

The following analyses will be conducted in the enrolled population. These analyses except listings will also be conducted by country.

- The presence or absence and nature of deviation will be tabulated in each treatment arm.

7.5. Analyses of Patient Baseline Characteristics

The following analyses will be conducted in the AT and FAS populations. These analyses except listings will also be conducted by country.

- For the baseline characteristic factors listed in Table 5-6 of Section “5.2.2 Patient Baseline Characteristics,” the number and proportion of subjects and summary statistics will be presented in each treatment arm.

7.6. Compliance Analyses

The following analyses will be conducted in the AT and FAS populations. These analyses except listings will also be conducted by country.

7.6.1. Dose Intensity

- The summary statistics of actual dose intensity and relative dose intensity and the number and proportion of subjects with each category of relative dose intensity (<80%, ≥80% to <90%, ≥90%) will be presented in each treatment arm.

7.6.2. Compliance

- The number and proportion of subjects with dose reduction, interruption, skip (only for L-OHP and CDDP), and prolongation of the recovery period (only for TAS-118 and S-1) will be calculated in each treatment arm. These analyses will be conducted for each cycle and for the overall cycles.

7.6.3. Discontinuation

- The presence or absence of study discontinuation and the reason for discontinuation will be tabulated in each treatment arm.
- A list of adverse events leading to discontinuation will be created in the enrolled population.

7.6.4. Cumulative Dose/Duration of Treatment

- The summary statistics of the total duration of treatment and cumulative dose will be presented by treatment arm and study drug. The total duration of TAS-118 and S-1 treatment will be calculated by dividing the sum of the number of doses by 2; the total duration of L-OHP and CDDP treatment will be the sum of the number of doses.

7.6.5. Treatment Completion

- The number of subjects who completed the treatment in each cycle will be tabulated by treatment arm. Subjects who received doses of each drug that are not less than the doses specified below in one cycle are regarded as those who completed the treatment and otherwise as those who did not complete the treatment. The doses required for completion are presented in Table 7-1.

Table 7-1 Doses required for completion

TAS-118	14 packages
S-1	84 capsules (at a dose of 40 or 50 mg at the start of cycle) 126 capsules (at a dose of 60 mg at the start of cycle)
L-OHP and CDDP	1 dose

7.6.6. Treatment Cycle

- The summary statistics of the number of subjects in each cycle and the last cycle number in each subject will be presented by treatment arm.

7.6.7. Proportion of Outpatient Visits

- The summary statistics of the proportion of outpatient visits will be presented by treatment arm. The proportion of outpatient visits will be calculated as follows. In this calculation, the cutoff date is defined as the data cutoff date recorded in the data cutoff date decision record. The definition of hospitalization and the last dose is presented in Table. 7-2.

$$\text{Proportion of outpatient visits: } 100\% - \frac{\text{Duration of hospitalization}}{\text{Duration of treatment}} \times 100$$

Duration of hospitalization: End date of hospitalization – Start date of hospitalization + 1
(If a subject experienced more than one hospitalization, add up the durations of hospitalization)

Duration of treatment: Date of the last treatment – Start date of Cycle 1 treatment + 1

Table 7-2 Definition of hospitalization and last treatment

Start date of hospitalization	If a subject is hospitalized before the start date of Cycle 1 treatment, the duration is defined as the time from the start date of Cycle 1 treatment.
End date of hospitalization	In a subject who discontinued the treatment and is still hospitalized after the date of the last treatment, the date of the last treatment is defined as the end date of hospitalization. In a subject who continues to receive the study drug as of the data cutoff date, the data cutoff date is defined as the end date of hospitalization.
Date of the last treatment	In a subject who continues to receive the study drug as of the data cutoff date, the data cutoff date is defined as the date of the last treatment.

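### SAP 7.6.7, Table 7-2: for a subject still on drug at cutoff, completed hospital stays are extended to the cutoff date, and stays that begin after the last treatment are not excluded, so some outpatient proportions are wrong and can fall below 0%

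*SAP*

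**What the plan says.** SAP 7.6.7 takes the ratio of hospital time to treatment time, as a percentage, away from 100%.

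- Numerator, per stay: "Duration of hospitalization: End date of hospitalization – Start date of hospitalization + 1". For several stays: "If a subject experienced more than one hospitalization, add up the durations of hospitalization".
- Denominator: "Duration of treatment: Date of the last treatment – Start date of Cycle 1 treatment + 1". For a subject still on study drug at cutoff, "the data cutoff date is defined as the date of the last treatment".

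Table 7-2 then adjusts the dates of stays.

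- Start: "If a subject is hospitalized before the start date of Cycle 1 treatment, the duration is defined as the time from" Cycle 1 Day 1.
- End, treatment stopped: the end moves to the last treatment date, on the condition "In a subject who discontinued the treatment and is still hospitalized after the date of the last treatment".
- End, still on study drug: "as of the data cutoff date, the data cutoff date is defined as the end date of hospitalization". No condition about being in hospital is attached.

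No row covers a stay that begins after the last treatment date. Protocol Table 11.1-1 lists the admission date, the reason for admission and the discharge date among the data collected, so the true end of a completed stay is available.

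**The concern.** The two end-date sentences sit in the same cell, but only the one for subjects who stopped treatment requires that the stay is still open. The other applies to any stay of a subject who remains on drug. It therefore replaces a recorded discharge date with the cutoff, and because stays are summed, the same calendar days are counted several times. Repeat short admissions are plausible: protocol 15.1.3 foresees hospitalization for study treatment and procedures.

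The missing row has a different effect. Time in hospital after treatment ended can be set against a denominator that ended earlier.

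What is at stake is one compliance table. SAP 7.6.7 gives no purpose for it, but a reader is likely to use it to compare how far each regimen can be given to outpatients, since protocol 2.2 notes that CDDP needs hydration and L-OHP does not. The table reports summary statistics, which SAP 5.2.3.1 defines to include the minimum, mean and standard deviation, and SAP 7.6 repeats the analysis by country. A few values far below zero would damage those figures, while the median and quartiles would move little.

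**Working it through.** The SAP gives no numerical result for this measure, so there is no figure to reproduce. The check applies the SAP formula to illustrative records. All day numbers are assumptions, and Day 1 is Cycle 1 Day 1.

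**Formula.** Proportion = 100 - 100 × Σ(end - start + 1) / T, where T is the day of last treatment, or the cutoff day if the subject is still on drug.

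**A. Still on drug at cutoff, end date set to T for every stay**

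| Record | Hospital days as written | As written | True hospital days | True value |
|---|---|---|---|---|
| T = 900; 3-day stays from Days 1, 36, 71 | 900 + 865 + 830 = 2,595 | 100 - 288.3 = -188.3% | 9 | 99.0% |
| T = 210; one stay, Days 8-12 | 203 | 100 - 96.7 = 3.3% | 5 | 97.6% |
| T = 210; two 5-day stays from Days 8, 43 | 203 + 168 = 371 | 100 - 176.7 = -76.7% | 10 | 95.2% |
| T = 210; three 5-day stays from Days 8, 43, 78 | 203 + 168 + 133 = 504 | 100 - 240.0 = -140.0% | 15 | 92.9% |

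With one stay starting on Day s, the value as written is 100 × (s - 1)/T. It cannot be negative, but it depends only on the admission day and not on the length of the stay. With two stays starting on Days s1 and s2, the extended lengths sum to 2T - s1 - s2 + 2. This exceeds T, and the proportion falls below zero, whenever s1 + s2 < T + 2.

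**B. Treatment stopped, stay begins after last treatment, discharge date kept**

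- T = 91, stay Days 100-113: 14 hospital days; 100 - 100 × 14/91 = 84.6%. No hospital day falls in the treatment period, so the true value is 100%.
- T = 21, stay Days 25-50: 26 hospital days; 100 - 100 × 26/21 = -23.8%. The true value is again 100%.

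**C. Stays that Table 7-2 handles correctly**

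- T = 100, stay Days 95-110: the end moves to Day 100, leaving 6 days, and 100 - 6 = 94.0%, which is right.
- A stay that straddles Cycle 1 Day 1 has its start moved to that day, which is also right.
- T = 210, still on drug and still in hospital at cutoff, admitted Day 205: 6 days, 97.1%. Here the cutoff rule does what it should.

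**The case against.** The best reply is that Table 7-2 is a list of exceptions. It gives no end date for an ordinary completed stay, so a programmer must already be using the recorded discharge date, and the cutoff sentence can be read in parallel with the one before it, as meaning still in hospital at cutoff. That is probably what the authors meant. It does not settle the matter, because the condition is written into one sentence and absent from the next. Nor does it deal with stays that begin after the last treatment.

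Three stronger readings are tempting, and the documents do not support them.

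- **Values above 100%.** Moving the end of a post-treatment stay back to the last treatment date gives 91 - 100 + 1 = -8 days and 108.8% in the first record of part B. But the rule applies only to someone still in hospital after the last treatment, and a patient first admitted later does not fit that condition. A stay that ended before Cycle 1 is similar: the rule counts time from Cycle 1 Day 1, and such a stay has none.
- **Unlimited hospital time after treatment.** The discharge date still ends the stay. The defect is that the stay is not limited to the treatment period.
- **A bias between arms.** Suppose treatment time is exponential with the phase II PFS medians in protocol 2.4 (8.3 and 5.6 months), accrual lasts 19 months and cutoff falls at month 44. Then about 6.2% and 1.7% would still be on drug at cutoff; at a median of 4 months it would be 0.4%. The 44 months is an assumption. Treatment also stops for reasons other than progression (protocol 13.1.1). No direction or size of an arm difference follows.

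It is also fair to say that the frequency of post-treatment stays is unknown. Protocol Table 11.1-1 sets no time limit on hospitalization data, but the schedule tables have no row for it.

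**Conclusion.** The concern stands in two parts. First, the cutoff sentence in Table 7-2 is wrong as written: for a subject still on study drug it overrides known discharge dates, badly understates the proportion after one early stay, and can take it below 0% with two or more. Second, the table leaves out stays that begin after the last treatment. Read literally, their full length counts against a treatment period that contains none of it.

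The per-record errors are exact arithmetic on assumed dates. How many subjects are affected cannot be determined from the documents. The severity is minor: the measure is not among the endpoints in SAP 5.1.1 or protocol 5.1, no test is planned on it in SAP 7.6.7, and OS, alpha and power are unaffected.

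**What to change.** Replace the start and end rows of Table 7-2 with one rule: hospital days are the distinct calendar days in hospital from Cycle 1 Day 1 to the last treatment date, or to the data cutoff if the subject is still on study drug.

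Per stay: max(0, min(discharge, last treatment or cutoff) - max(admission, Cycle 1 Day 1) + 1).

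Use the cutoff as the end date only for a stay still open at cutoff, and count a day shared by two stays once. Every value then lies between 0% and 100%. The part A records return 99.0%, 97.6%, 95.2% and 92.9%, both part B records return 100%, and the part C results do not change.

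The cost is a wording change through the revision route in SAP Section 8 and one line of derivation code. No new data are needed.

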7.7. Concomitant Medications

- The use of concomitant medications will be tabulated by Generic Medication Name of WHO Drug Dictionary in each treatment arm.

7.8. Subsequent Therapy

- The number and proportion of subjects who used subsequent therapies listed in Table 7-3 will be tabulated in each treatment arm. This analysis will also be conducted by country.

Table 7-3 Subsequent therapy

Category	Details
Subsequent therapy	No, yes
Type of subsequent therapy	Chemotherapy, chemoradiotherapy, radiotherapy, immune/hormonal therapy, surgery, other
Detail of chemotherapy	Paclitaxel, Abraxane, docetaxel, irinotecan, S-1, capecitabine, 5-FU, UFT, oxaliplatin, cisplatin, leucovorin, trastuzumab, ramucirumab, nivolumab, other
Intent of surgery	Palliative, curative

7.9. Laboratory Values

The following analyses will be conducted in the AT population. These analyses except listings will also be conducted by country. The listings will be based on the enrolled population.

- The change in laboratory values over time from the start of each cycle in each subject will be graphed by treatment arm.
Laboratory values to be evaluated are hemoglobin, white blood cell count, neutrophil count, lymphocyte count, and platelet count.
- The minimum level of laboratory tests at predose and at each cycle in each subject will be identified by treatment arm, the summary statistics will be presented, and the levels will be summarized by grade.
Laboratory tests to be evaluated are hemoglobin, white blood cell count, neutrophil count, lymphocyte count, platelet count, albumin, Na, K, and corrected Ca.
- The maximum level of laboratory tests at predose and at each cycle in each subject will be identified by treatment arm, the summary statistics will be presented, and the levels will be summarized by grade.
Laboratory tests to be evaluated are AST, ALT, ALP, bilirubin, creatinine, Na, K, and corrected Ca.
- The worst level of urine protein at predose and at each cycle in each subject will be identified by treatment arm and summarized by category.
- The minimum level of laboratory tests throughout the study period in each subject will be identified by treatment arm, and the summary statistics will be presented for predose level, minimum level, the number of days to the minimum level, and cycle with the minimum level.
Laboratory tests to be evaluated are hemoglobin, white blood cell count, neutrophil count, and platelet count.
- The summary statistics will be presented for the minimum level of laboratory tests in subjects with grade 3 or higher reduction, the number of days from the start date of onset cycle to the minimum level, and the number of days required for recovery to grade 2 or less from the minimum level within an onset cycle in each treatment arm.
Laboratory tests to be evaluated are hemoglobin, white blood cell count, neutrophil count, and platelet count.
If grade 3 or higher reduction is observed in more than one cycle in the same subject, both decreased levels will be used for calculating the summary statistics.

Subjects who meet any of the following criteria will be regarded as those who are not recovered:

- After grade 3 or higher reduction, grade 2 or less is not measured within the same cycle.
- Measurement date of grade 2 or less reduction in laboratory values – date of the last study treatment ≥ 30 days

When the start date of subsequent therapy \leq date of the last study treatment + 30 days is met, the following criterion will be used:

Measurement date of grade 2 or less reduction in laboratory values \geq start date of subsequent therapy

- After “grade 3 or higher reduction” is replaced with “grade 2 or higher reduction” and “recovery to grade 2 or less” is replaced with “recovery to grade 1 or less,” the same analyses as specified above will be conducted.

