10.1.2.1 Arm A (TAS-118/L-OHP)

L-OHP will be administered on Day 1, and TAS-118 will be administered orally twice daily in a administration period from Day 1 through Day 7 followed by a recovery period from Day 8 through Day 14. This regimen is to be repeated every 2 weeks until study treatment discontinuation criteria (Section 13.1.1). If TAS-118 administration is initiated from evening on Day 1, it will be continued until morning on Day 8, and recovery period will be from evening on Day 8 through morning on Day 15 (see Figure 10.1.2.1-1).

- A recovery period is not allowed to be shortened (e.g. even if the dosing is interrupted due to some reasons, such as adverse events after the morning of Day 6, the subsequent dosing should be started as a new treatment cycle after the morning/evening meal on Day 15).
- Any unused doses are not allowed to be administered in a recovery period (see Figure 10.1.2.1-2).
- If any of dose initiation criteria (see Table 10.1.3.1-1) for L-OHP did not meet, administration of L-OHP may be skipped and start each treatment cycle only with TAS-118.

[figure not shown]

Figure 10.1.2.1-1 Study regimen of TAS-118/L-OHP

[figure not shown]

Figure 10.1.2.1-2 Study regimen of TAS-118

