10.1.2.2 Arm B (S-1/CDDP) [CDDP on Day 1] (Korea)

CDDP will be administered on Day 1, and S-1 will be administered orally twice daily in a administration period from Day 1 through Day 21 followed by a recovery period from Day 22 through Day 35. This regimen is to be repeated every 5 weeks until study treatment discontinuation criteria (Section 13.1.1). If S-1 administration is initiated from evening on Day 1, it will be continued until morning on Day 22, and recovery period will be from evening on Day 22 through morning on Day 36 (see Figure 10.1.2.2-1).

- A recovery period may be shortened down to 7 days after the administration period which has been finished either without AE/SAE related to study drug or with AE/SAE related to study drug that are of no safety concern and assessed as allowing the subsequent recovery period to be shortened (see Figure 10.1.2.2-2Figure 10.1.2.2-3).
- Any unused doses are not allowed to be administered in a recovery period (see Figure 10.1.2.2-3).
- If the dose interruption continues 14 days and over in the administration period, drug administration has to be discontinued in the cycle. After confirmation of being met criteria for starting new treatment cycle (see Table 10.1.3.1-2), drug administration can be restarted as the next treatment cycle (see Figure 10.1.2.2-4).
- If any of dose initiation criteria for CDDP(see Table 10.1.3.1-2) did not meet, administration of CDDP may be skipped and start each treatment cycle only with S-1.

[figure not shown]

Figure 10.1.2.2-1 Study regimen of S-1/CDDP

[figure not shown]

Figure 10.1.2.2-2 Study regimen of S-1 (1)

[figure not shown]

Figure 10.1.2.2-3 Study regimen of S-1 (2)

[figure not shown]
[figure not shown]
[figure not shown]
[figure not shown]
[figure not shown]

Figure 10.1.2.2-4 Study regimen of S-1 (3)

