11.4 Tests during Study Treatment

Arm A (TAS-118/L-OHP)

- (1) Before initiation of next treatment cycle (Day15) (from Day 14 to Day 18 if not feasible on Day 15)
 - Hematology, serum chemistry, urinalysis, physical examination, AE/SAE assessment, concomitant medications
 - Examination is mandatory on Day1 or the day before starting study treatment specified in this protocol.
- (2) If initiation of next treatment cycle is postponed
 - Hematology, serum chemistry, urinalysis, physical examination, AE/SAE assessment, concomitant medications
 - Every 1 week starting on Day 1 of each treatment cycle (the data may be collected within 7 days before the scheduled date).
- (3) If any of abnormality is suspected (if necessary)
 - Weight, body temperature, blood pressure, ECOG PS, electrocardiography

- (4) Every 6 weeks from the day of randomization (within 1 week before or after the scheduled date)

- Tumor measurement, tumor markers

If PD is strongly suspected by any symptoms or signs, perform extra tumor measurement objectively at the discretion of the investigator (or subinvestigator) even if not the scheduled date.

In case of performing extra tumor measurement, the measurement of the tumor marker is not mandatory.

Arm B (S-1/CDDP) [CDDP on Day1] (Korea)

- (1) Day 15 in each cycle (from Day 8 to Day 22 if not feasible on Day 15)
- Physical examination, hematology, serum chemistry, urinalysis, AE/SAE assessment, concomitant medications
- (2) Before initiation of next treatment cycle (Day36) (from Day 29 to Day 43 if not feasible on Day 36)
- Hematology, serum chemistry, urinalysis, physical examination, AE/SAE assessment, concomitant medications
 - Examination is mandatory on Day1 or the day before starting study treatment specified in this protocol.
- (3) If initiation of next treatment cycle is postponed
- Hematology, serum chemistry, urinalysis, physical examination, AE/SAE assessment, concomitant medications
 - Every 1 week starting on Day 1 of each treatment cycle if the next treatment cycle is delayed (the data may be collected within 7 days before the scheduled date).
- (4) If any of abnormality is suspected (if necessary)
- Weight, body temperature, blood pressure, ECOG PS, electrocardiography
- (5) Every 6 weeks from the day of randomization (within 1 week before or after the scheduled date)
- Tumor measurement, tumor markers

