If PD is strongly suspected by any symptoms or signs, perform extra tumor measurement objectively at the discretion of the investigator (or subinvestigator) even if not the scheduled date.

In case of performing extra tumor measurement, the measurement of the tumor marker is not mandatory.

Arm B (S-1/CDDP) [CDDP on Day8] (Japan)

- (1) Day 8 in each cycle (on the day before administration or on the day of administration until the start of administration) (from Day 6 to Day 15 if not feasible on Day 8)
- Physical examination, hematology, serum chemistry, urinalysis, AE/SAE assessment, concomitant medications

- (2) Day 15 in each cycle (from Day 8 to Day 22 if not feasible on Day 15)
 - Physical Examination, Hematology, serum chemistry, urinalysis, AE/SAE assessment, concomitant medications
- (3) Before initiation of next treatment cycle (Day36) (from Day 29 to Day 43 if not feasible on Day 36)
 - Hematology, serum chemistry, urinalysis, physical examination, AE/SAE assessment, concomitant medications
 - Examination is mandatory on Day1 or the day before starting study treatment specified in this protocol.
- (4) If initiation of next treatment cycle is postponed
 - Hematology, serum chemistry, urinalysis, physical examination, AE/SAE assessment, concomitant medications
 - Every 1 week starting on Day 1 of each treatment cycle if the next treatment cycle is delayed (the data may be collected within 7 days before the scheduled date).
- (5) If any of abnormality is suspected (if necessary)
 - Weight, body temperature, blood pressure, ECOG PS, electrocardiography
- (6) Every 6 weeks from the day of randomization (within 1 week before or after the scheduled date)
 - Tumor measurement, tumor markers

If PD is strongly suspected by any symptoms or signs, perform extra tumor measurement objectively at the discretion of the investigator (or subinvestigator) even if not the scheduled date.

In case of performing extra tumor measurement, the measurement of the tumor marker is not mandatory.

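### The by-cycle laboratory grade tables in SAP 7.9 are not comparable between arms: an Arm A cycle has one scheduled sample in 14 days, an Arm B cycle two or up to three in 35 days.

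*SAP*

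**What the plan says.** **Analysis (SAP 7.9).** For haemoglobin, white cells, neutrophils, lymphocytes, platelets, albumin, Na, K and corrected Ca: "The minimum level of laboratory tests at predose and at each cycle in each subject will be identified by treatment arm". For corrected Ca, Na, K, AST, ALT, ALP, bilirubin and creatinine: "The maximum level of laboratory tests at predose and at each cycle in each subject will be identified by treatment arm". Both sets are summarised by grade in the as-treated population, overall and by country. SAP 7.9 adjusts for neither cycle length nor number of samples.

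The same section also plans each subject's minimum over the whole study for haemoglobin, white cells, neutrophils and platelets. It is given as summary statistics, with no table by grade stated and no matching maximum.

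**Cycle length (Protocol 10.1.2).** Arm A: "This regimen is to be repeated every 2 weeks until study treatment discontinuation criteria". Arm B in Korea: "This regimen is to be repeated every 5 weeks until study treatment discontinuation criteria". Japan has the same five-week cycle. In Arm B, "A recovery period may be shortened down to 7 days after the administration period", so a cycle can be 28 days.

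**Sampling (Protocol 11.4).**
- Arm A: "Before initiation of next treatment cycle (Day15) (from Day 14 to Day 18 if not feasible on Day 15".
- Arm B, both countries: "Day 15 in each cycle (from Day 8 to Day 22 if not feasible on Day 15", plus a sample before the next cycle, nominally Day 36.
- Arm B, Japan, in addition: "Day 8 in each cycle (on the day before administration or on the day of administration until the start of administration". Footnote i of Table 11.2-2 makes this examination mandatory when cisplatin is given, and footnote j requires the Day 15 data to be kept separate from Day 8.

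**Assignment to cycles (SAP 5.2.1.1.3).** A sample taken before dosing on the first day of a cycle counts towards the preceding cycle, so it adds nothing to the new one.

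**The concern.** A cycle is not the same unit of observation in the two arms. It differs in length (14 against 35 days) and in the number of chances to record a low or high value. Taking the worst value within a cycle turns that difference into an apparent difference in toxicity, even if the laboratory values behave identically.

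Timing adds to this. Arm A's only routinely scheduled sample comes after the Day 8–14 recovery period. Arm B is also sampled on Day 15, and in Japan on Day 8, while S-1 is still being taken.

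Safety is a stated secondary comparison (Protocol 4.2, SAP 1.2). For liver tests, creatinine, albumin, lymphocytes and electrolytes, the by-cycle table is the only graded laboratory summary that SAP 7.9 specifies. A reader who compares its columns across arms would be comparing sampling schedules as well as treatments.

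**Working it through.** The plan states no figure on this point that could be reproduced. The check counts scheduled samples and works out what the per-cycle worst value does at equal risk.

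**Step 1: scheduled samples per cycle, k.** From Protocol 11.4 and the assignment rule in SAP 5.2.1.1.3:

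| | Cycle length | Scheduled days | k |
|---|---|---|---|
| Arm A | 14 days | 15 | 1 |
| Arm B, Korea | 35 days | 15, 36 | 2 |
| Arm B, Japan (cisplatin given) | 35 days | 8, 15, 36 | 3 |

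**Step 2: chance of at least one Grade 3 or higher value per cycle.** Let p be the chance at any one sample, the same in both arms. The documents do not give p, so it is an assumption. With independent samples the chance is 1 − (1 − p)^k:

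| p | Arm A | Korea | Japan |
|---|---|---|---|
| 2% | 2.0% | 4.0% | 5.9% |
| 5% | 5.0% | 9.8% | 14.3% |
| 10% | 10.0% | 19.0% | 27.1% |
| 20% | 20.0% | 36.0% | 48.8% |

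For example, at p = 10%: 1 − 0.9² = 0.19 and 1 − 0.9³ = 0.271.

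**Step 3: allow for correlation within a cycle.** Samples from one patient are correlated, and the documents do not say how strongly. Each value was taken as standard normal with common correlation ρ, and Grade 3 or higher as falling below the p-quantile (1,000,000 simulated draws):

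| p | ρ | Arm A | Korea | Japan |
|---|---|---|---|---|
| 10% | 0.5 | 10.0% | 16.8% | 21.9% |
| 10% | 0.9 | 10.0% | 13.1% | 15.0% |
| 5% | 0.5 | 5.0% | 8.8% | 11.8% |
| 5% | 0.9 | 5.0% | 6.8% | 7.9% |

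The mean per-cycle minimum, in standard deviations from the mean of a single sample, moves in the same way: 0 / −0.56 / −0.84 at ρ = 0, 0 / −0.40 / −0.60 at ρ = 0.5, and 0 / −0.18 / −0.27 at ρ = 0.9.

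**Step 4: does a common time base remove it?** Over 35 days Arm A has 35/14 = 2.5 scheduled samples, against 2 (Korea) and 3 (Japan). Over 70 days (five Arm A cycles, two Arm B cycles) the counts are 5, 4 and 6. At p = 10% with independence:
- Arm A: 1 − 0.9⁵ = 41.0%
- Korea: 1 − 0.9⁴ = 34.4%
- Japan: 1 − 0.9⁶ = 46.9%

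Arm A now lies between the two control schedules, so the one-directional tilt against Arm B is gone. A smaller difference between the country schedules remains.

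**The case against.** The best defence is that SAP 7.9 already has a summary that is not per cycle: the whole-study minimum for haemoglobin, white cells, neutrophils and platelets. The adverse event tables in SAP 7.2.1 are also per subject and by grade, and clinically significant laboratory abnormalities enter them (Protocol 15.1.1 and 15.2.1). The by-cycle tables carry no planned between-arm test. A per-cycle worst grade has its own use, since dose reduction in both arms refers to the worst grade in the last cycle (Protocol 10.1.3.3 and 10.1.3.4). SAP section 9 adds that only representative analyses are listed and that the rest are in a separate output plan.

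Much of this stands and limits the point. It does not remove it. The whole-study minimum states no table by grade and leaves out every chemistry test, albumin, lymphocytes and electrolytes. The adverse event tables take in only those laboratory changes judged clinically significant. The output plan is not among the documents.

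Three stronger readings are tempting, and the documents do not support them:
- **That every Arm A value is taken after the recovery week.** Only the routine scheduled sample is. Weekly samples are added when a cycle is delayed (Protocol 11.4), interruption and resumption depend on blood counts (Protocol 10.1.3.2), and end-of-treatment and follow-up samples fall into the last cycle (SAP 5.2.1.1.3).
- **That Japanese controls will look worse than Korean controls.** Japan has the extra sample, but it is taken before cisplatin, and Day 15 is nominally 14 days after cisplatin in Korea and 7 in Japan. With assumed risks of 15% and 3% at Days 15 and 36 in Korea, the per-cycle rate is 1 − 0.85 × 0.97 = 17.6%. With 2%, 8% and 3% at Days 8, 15 and 36 in Japan it is 1 − 0.98 × 0.92 × 0.97 = 12.5%. The order reverses, so no direction can be claimed.
- **That 70-day blocks alone settle the matter.** With 28-day Arm B cycles, 70 days is 2.5 cycles. A table of pre-next-cycle samples has its own imbalance: 7 recovery days in Arm A against up to 14 in Arm B.

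**Conclusion.** The point holds as a statement about comparability. At equal risk per sample, the scheduled sampling alone makes the by-cycle Grade 3 or higher rate higher in Arm B. At an assumed 10% per sample the rate is about 1.3 to 1.9 times that of Arm A in Korea and 1.5 to 2.7 times in Japan, for correlation from 0.9 to 0.

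Those sizes rest on assumed risks and correlations and on scheduled counts. Delay samples, unscheduled tests, skipped cisplatin and 28-day cycles all change the counts. The calculation shows what sampling contributes; it does not predict the observed tables, because true risks differ by treatment and by day.

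The effect is on the interpretation of descriptive safety tables, mainly for tests other than the four with a whole-study minimum. The overall survival analysis is untouched.

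**What to change.** In SAP 7.9:

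1. Extend the whole-study minimum to a table of worst grade per subject over the treatment period, up to the end of the cycle decision period in SAP 5.2.1.1.3. Cover all listed laboratory tests, minima and maxima, by arm and country.
2. Show beside it, by arm and country, the number of samples and the treatment duration per subject.
3. Name this table as the one for between-arm comparison of laboratory toxicity.
4. Keep the by-cycle tables as within-arm descriptions, with a footnote that cycle length and sampling differ and that they are not comparable between arms.
5. Optionally, add a table on a common calendar window, such as 70 days from first dose, as support.

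The cost is table programming on data already collected, through the revision route in SAP section 8. Some imbalance stays: treatment duration may differ between arms, the Japanese and Korean schedules still differ, and low points in Arm A that fall between scheduled samples remain unseen. Reporting sample counts and duration lets the reader judge the first two.
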